5.1.4. Descriptive Statistics

By default, descriptive statistics for continuous variable include: n , Mean, Standard Deviation (STD), Q1 and Q3, Median, Minimum (Min), and Maximum (Max). Unless specified in the actual table shells, the mean, median, Q1 and Q3 should be displayed to the one more decimal place than the original data (derived analysis data). Standard deviation should be displayed to the two more decimal places than the original data (derived analysis data). The minimum and maximum should be displayed to the same number of decimal places as the original data.

5.2. Analysis Populations

5.2.1. Intent to Treat Population

The intent to treat (ITT) Population will include all randomized subjects. The primary efficacy analyses will be performed on the ITT Population.

5.2.2. Efficacy Evaluable Population

The supportive efficacy analyses will be performed on the efficacy evaluable (EE) population, which will include all ITT subjects who completed 6 cycles of treatment, unless they have established an earlier response or who discontinued the study due to death or disease progression. Subjects assigned to Arm A, who received less than 3 cycles of durvalumab and continued under azacitidine monotherapy are to be excluded from the EE population.

An earlier response is defined as CR, mCR, PR or HI before the end of cycle 6 for the MDS cohort or CR and CRi before the end of cycle 6 for the AML cohort.

Subjects who do not have an on-treatment disease assessment and discontinue due to death or disease progression without post baseline response assessment will be considered as nonresponders.

5.2.3. Safety Population

The Safety Population will include all subjects who take at least 1 dose of any study drug.

5.2.4. Pharmacokinetic Population

Not applicable. The PK analyses will be performed by the Celgene TD group.

5.3. Definitions

5.3.1. Date of First Administration of Study Treatment

The date of first administration of study treatment is derived as the first date that durvalumab, or azacitidine was administered.

For simplicity, the date of first administration of study treatment will also be referred as the start date of study treatment.

5.3.2. Date of Last Administration of Study Treatment

The date of last administration of study treatment is the last date that durvalumab or azacitidine was administered.

5.3.3. Study Day

The study day will be calculated as specified in [Section 5.1.2](#) and will be displayed in the data listings.

5.3.4. Baseline

Baseline values are defined as the last assessment of a particular parameter (eg, vital signs, weight, or laboratory assessments) prior to administration of the subject's first dose of any study drug, unless noted otherwise for a particular assessment. In most cases, baseline assessments are those performed before dosing on Cycle 1, Day 1. However, the last measurement on or prior to the randomization date will be used as the baseline value for subjects who did not take any study drug. Unless otherwise specified in the derived data set specification, the baseline disease characteristics, baseline laboratory value and vital sign that are used in the safety analyses will be derived using this method.

Since the hemoglobin value can be influenced by a red blood cell (RBC) transfusion, the hemoglobin (Hgb) values used in some efficacy analyses are required to satisfy the 7/3-day rule below:

- 7/3-day rule: Only hemoglobin values that are at least 7 days after a transfusion may be used unless there is another transfusion within 3 days after the hemoglobin assessment.

In efficacy analyses, after applying above 7/3-day rule, the baseline hemoglobin value is defined as the last hemoglobin value in 56-days on or prior to randomization.

6. SUBJECT DISPOSITION

Reasons for screen failure will be summarized and listed. Enrollment by country and sites will be summarized by treatment arm within each disease cohort.

A summary of subject disposition (analysis population allocation, subjects randomized, subjects discontinued, along with primary reason for treatment discontinuation and study discontinuation) will be presented for the ITT Population and for the Safety Population and will be summarized using frequencies for both Treatment and Follow-up Periods.

Reasons for discontinuing study treatment will be collected on the CRF and will be summarized for all randomized subjects with the following categories:

- Completed
- Death
- Adverse event
- Progressive disease
- Lack of efficacy
- Withdrawal by subject
- Lost to follow-up
- Protocol violation
- Other

Reasons for discontinuing the study (ie, no follow-up visit and no longer participating in the study) will be collected on the CRF and will be summarized for all randomized subjects with the following categories:

- Completed (per protocol)
- Death
- Adverse event
- Withdrawal by subject
- Lost to follow-up
- Other

Protocol violations / deviations will be summarized and listed by disease cohort and treatment arm for the ITT Population. Protocol violation / deviation will be reported and monitored throughout the study. Data of protocol violation / deviation will be finalized prior to database lock.

The following by-subject listing of subjects with demographic information will be provided:

- Subject listing of discontinuation.

- Subject listing of screen failures.
- Subject listing of protocol violations and protocol deviations.
- Subject listing of being excluded from ITT, EE, Safety or PK Population.

CELGENE PROPRIETARY INFORMATION

7. DEMOGRAPHICS AND BASELINE CHARACTERISTICS

Summaries using descriptive statistics for the demographics and baseline characteristics will be carried out by disease cohort and treatment arm for each analysis population defined in [Section 5.2](#). Listings will be presented for the ITT Population. Continuous variables will be summarized using descriptive statistics and categorical variables will be summarized with frequency counts and percentages.

7.1. Background and Demographic Characteristics

Age at time of consent (years), weight (kg), height (cm), body mass index (BMI), body surface area (BSA) and other continuous demographic will be summarized using descriptive statistics (eg, mean, standard deviation [STD], median, minimum [Min] and maximum [Max]), while age category (<65 ; ≥ 65 - <75; ≥75), gender, race and other categorical variables will be summarized with frequency counts and percentages.

The below formulas will be used:

$BMI (kg/m^2) = \text{weight (kg)} / (\text{height} * \text{height (m}^2))$.

$BSA (m^2) = (\text{weight (kg)}^{0.425}) * (\text{height (cm)}^{0.725}) * 0.007184$.

7.2. Baseline Characteristics

Baseline clinical characteristics include temperature (°C), systolic blood pressure (SBP, mmHg), diastolic blood pressure (DBP, mmHg), pulse (bpm), respiratory rate, Eastern Cooperative Oncology Group (ECOG) performance status (PS) and baseline electrocardiograms (ECGs) will be summarized.

Coagulation test performed at screening will be summarized. Overall interpretation from coagulation test will be summarized along with prothrombin time/international normalized ratio, activated partial thromboplastin time, and thrombin time.

Baseline laboratory assessments from central laboratory will be summarized for Hgb, platelet count, absolute neutrophil count (ANC), white blood cell (WBC) count, creatinine, aspartate aminotransferase (AST/SGOT), alanine aminotransferase (ALT/SGPT) and total bilirubin.

Creatinine clearance (CrCl) will be assessed at screening by the central laboratory. Creatinine clearance is estimated using the Cockcroft-Gault formula where $CrCl(mL/min) = (140 - \text{age}) (\text{weight [kg]}) / 72 (\text{serum creatinine [mg/dL]})$; for females, the formula is multiplied by 0.85 (Cockcroft, 1976). The CrCl will be summarized as continuous variable. The creatinine clearance will be normalized to an average surface area (size) of 1.73m². The corrected CrCl will be summarized as continuous variable and category variable defined as chronic kidney disease (CKD) stages (Stage 1, 90+; Stage 2, 60-89; Stage 3, 30-59; Stage 4, 15-29; Stage 5, <15).

Cytogenetic risk classifications ([Appendix 17.4](#) and [17.5](#)) will be summarized with frequency counts and percentages. For MDS cohort, IPSS-R will be summarized along with hemoglobin, platelet and absolute neutrophil count used in the derivation. Bone marrow blast will be summarized as continuous variable and category variable as defined in IPSS-R ($\leq 2\%$; $> 2\% - < 5\%$; $\geq 5\% - \leq 10\%$; $>10\%$).

Baseline RBC transfusion burden and platelet transfusion burden will be summarized. The baseline transfusion burden is defined the total number of units of transfusion received before or on the first dose date. Only RBC transfusions given for hemoglobin of ≤ 9.0 g/dL before or on the first dose date will count in the baseline RBC transfusion burden.

The time from initial diagnosis to randomization will also be summarized.

7.3. Medical History

Medical history will be coded using the Medical Dictionary for Drug Regulatory Activities (MedDRA) Version 19.0, or higher. Individual subject listings will be provided. System organ class (SOC) and preferred term (PT) will be summarized by frequency and percentage. Tables will be provided for subjects in the ITT Population and the Safety Population.

7.4. Prior Medications

Prior medications are defined as medications that were started before the start of study treatment (regardless of whether or not they are stopped before the start of the study treatment). Prior medications that are ongoing at the start date of study treatment will also be reported as concomitant medications.

The Anatomical Therapeutic Chemical (ATC) coding scheme of the World Health Organization (WHO) (September 2016 version, or higher) will be used to group medications into relevant categories. All prior medications will be summarized by ATC level 1, ATC 3 term term and preferred name in frequency tabulations for the ITT Population and the Safety Population.

7.5. Prior Anticancer Therapy

Whether subject had prior cancer surgery, prior radiation therapy, prior systemic anticancer therapy, prior stem cell transplantation, and prior hormonal anticancer therapy will be summarized with frequency counts and percentages in the ITT population. The number of prior systemic anticancer regimens will be summarized descriptively. In addition, prior exposure to anticancer systemic therapies will also be summarized by ATC level 1 term, ATC 3 term and preferred name with frequency counts and percentages in the ITT Population and the Safety Population.

8. STUDY TREATMENTS AND EXTENT OF EXPOSURE

Study treatment and extent of exposure summaries will be provided based on the Safety Population. Descriptive statistics will be provided for treatment exposure, cumulative dose, average daily dose, treatment compliance, dose intensity, relative dose intensity and dose modifications by disease cohort and treatment arm. Related summary will be provided for each treatment arm across the two disease cohorts. Individual subject listings will be provided to support the tables.

8.1. Treatment Exposure and Duration

Treatment exposure and number of days dosed will be summarized. Total treatment exposure (days) for each study drug is defined as follows:

- Azacitidine: date of first dose through date of last dose + 28 days;
- Durvalumab: date of first dose through date of last dose + 90 days.

Treatment exposure for subjects in the azacitidine alone arm is same as the treatment exposure of azacitidine. Treatment exposure for subjects in the combination arm is defined as date of first dose of any study drug through later one of date of last dose azacitidine + 28 days and date of last dose durvalumab + 90 days. Duration of exposure will be summarized for each arm.

Total number of days dosed is defined as the total number of days with a nonmissing dosing date.

See [Section 5.1.3](#) for cycle definition. Average cycle length (days) and number of treatment cycles will be summarized for each study drug. For azacitidine, average number of days dosed per cycle will be summarized. The number of days dosed per cycle is defined as the number of days with a nonmissing dosing date within that cycle. For average cycle length and average number of days dosed per cycle, a single average value will be computed for each subject and then the descriptive statistics will be provided. Additionally, the count and percent of subjects by number of cycles of treatment will be provided for each treatment.

For each study drug, duration of treatment (days) is defined as:

- (study drug end date) – (date of Cycle 1 Day 1) + 1.

Study drug end date is defined as Min [last non-zero/non-missing dose date + number of days to be covered by the last dose, death date].

The number of days to be covered by the last dose is defined in the [table 3](#).

Table 3: Number of days to be covered by the last dose

IP	Schedule	n = days to be covered by the actual last dose (if schedule respected) *
Durvalumab	CxD1	n=27
Azacitidine	CxD1 to CxD7	n=21

* if schedule is not respected the number of days to be covered by the actual last dose will be adapted accordingly so that the last dose date + n corresponds to the study day 28 of the cycle.

8.2. Cumulative Dose:

The cumulative dose during the treatment is defined as the sum of all doses taken across the treatment period (in mg). Cumulative dose will be calculated separately for azacitidine and durvalumab.

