5.1.3. Calculation of Cycles

The start date of each treatment cycle will be calculated based on study drug exposure records for each subject. The start date of the first cycle will be the date when the subject receives any dose of study drug. First dose date of Durvalumab infusion or azacitidine injection in each cycle will be considered as the start of the cycle.

Once the start dates, eg, $S_1, S_2, S_3 \dots$ are calculated, the end date of each cycle is calculated as the day before the start date of the following cycle, ie, $E_i = S_{i+1} - 1$. The last cycle in the treatment

phase is defined as the cycle with the last dose of any study drug. For the last cycle, the end date will be the last dose date plus 28 days or the death date, whichever is earlier.

The cycle number for each date of interest, eg, AE or lab, will be calculated based on the cycle window set by their start and end dates. If a date is on or after S_i and before S_{i+1} , the corresponding cycle number will be i .

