The adverse events of special interest (AESI) refer to a group of PTs from one or more SOCs relating to a defined medical condition or area of interest. Unless an AESI is defined by a single PT the AESI generally refers to a group of PTs, rather than the individual PTs.

AESIs will be summarized separately for azacitidine and durvalumab, The AESI summary for each study treatment will be summarized by AESIs, which will be referred as AESI categories in tables and listings, and by PT.

The following AESIs for azacitidine based on risk definitions (search criteria) as outlined in the Vidaza risk management plan (RMP) currently approved at the time of data cut-off will be summarized:

- Myelosuppression (Neutropenia, thrombocytopenia, anemia, general myelosuppression)
- Hemorrhagic events
- Infections
- Renal failure
- Hepatic failure
- Ischemic colitis
- Interstitial lung disease
- Cardiac events (cardiac failure, cardiac arrhythmias, myocardial infarction)
- Anxiety, confusional state, insomnia

- Other psychiatric disorders
- Tumour lysis syndrome
- Gastrointestinal disorders as defined by MedDRA SOC

Below are the AESIs for durvalumab for regulatory purposes:

- Adrenal insufficiency
- Colitis
- Dermatitis
- Diarrhoea
- Diabetes Mellitus Type 1
- Hyperthyroidism
- Hypophysitis
- Hypothyroidism
- Infusion related/Hypersensitivity/Anaphylactic reactions
- Select renal events
- Select pancreatic events
- Pneumonitis
- Rash
- Select hepatic events
- Other rare/miscellaneous

After review of the data, there may be other AESIs identified. The following summaries will be provided for TEAEs included in the above-mentioned AEs of special interest:

- All TEAEs
- All TEAEs by cycle of onset
- TEAEs of Grade 3
- TEAEs of Grade 4
- TEAEs of Grade 3 or 4
- Serious TEAEs
- TEAEs leading to study drug withdrawal
- TEAEs leading to study drug dose reduction
- TEAEs leading to study drug dose interruption

- TEAEs leading to death

The incidence rate per 100 person-years will also be derived for each AESI.

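### SAP 8.1 lets treatment exposure run 28 or 90 days past the last dose with no cap at death or data cut-off, so it counts days that were not observed, and usually more of them in Arm A

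*SAP*

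**What the plan says.** SAP 8.1 defines total treatment exposure per drug. For azacitidine it is "Azacitidine: date of first dose through date of last dose + 28 days" and for durvalumab "Durvalumab: date of first dose through date of last dose + 90 days". At arm level, "Treatment exposure for subjects in the azacitidine alone arm is same as the treatment exposure of azacitidine", while in the combination arm exposure ends at the "later one of date of last dose azacitidine + 28 days and date of last dose durvalumab + 90 days". None of these definitions mentions death or a data cut-off.

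Two neighbouring definitions do stop at death. For duration of treatment, also in SAP 8.1, "Study drug end date is defined as Min [last non-zero/non-missing dose date + number of days to be covered by the last dose, death date". In SAP 5.1.3, "For the last cycle, the end date will be the last dose date plus 28 days or the death date, whichever is earlier".

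SAP 12.1 adds one rate to the AESI tables: "The incidence rate per 100 person-years will also be derived for each AESI". It does not say which person-time is the denominator.

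**The concern.** Exposure is tabulated by cohort and arm. Followed literally, the SAP 8.1 rule credits a subject who dies inside the window with time after death. It also credits a subject still on treatment at a data cut-off with time that has not yet been observed.

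Both situations are foreseeable. SAP 12.1 plans a table of on-treatment deaths over the same 28- and 90-day windows. SAP section 2 plans analyses at interim, after 6 cycles and after 12 months, while treatment may continue beyond Cycle 6. Protocol 14.1 says that data generated after the final cut-off are not analysed and need not be entered in the eCRF, so days credited beyond that date carry no analysable events.

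The windows differ in length, so the error differs between arms. The direct consequence is an overstated exposure table, usually more so in Arm A. The possible further consequence is a lower AESI rate in Arm A, if this exposure serves as the person-time.

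**Working it through.** The plan states no figure to reproduce here. Its related Table 3 is consistent: day 1 + 27 and day 7 + 21 both give cycle day 28.

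**Where the window ends.** Durvalumab is given on day 1 and azacitidine on days 1 to 7 of a 28-day cycle (protocol 7.2.1). With both drugs fully dosed in the last cycle:
- Arm B: 7 + 28 = cycle day 35.
- Arm A: the later of 7 + 28 = 35 and 1 + 90 = 91, so cycle day 91.

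**Days credited after death.** Excess = window end minus day of death, with a minimum of 0.

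| Death on day of last cycle | Arm B | Arm A |
|---|---|---|
| 14 | 35 − 14 = 21 | 91 − 14 = 77 |
| 21 | 14 | 70 |
| 28 | 7 | 63 |
| 60 | 0 | 31 |

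Example: death on day 21 of Cycle 6 is study day 5 × 28 + 21 = 161. SAP 8.1 gives 140 + 35 = 175 days in Arm B and 140 + 91 = 231 in Arm A.

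**Days credited after cut-off.** For a subject on treatment, the same subtraction for a cut-off on days 8 to 28 of the current cycle gives 27 to 7 days in Arm B and 83 to 63 in Arm A. For instance, on day 14 of Cycle 7 the observed time is 6 × 28 + 14 = 182 days, against 168 + 35 = 203 (Arm B) and 168 + 91 = 259 (Arm A).

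**When the arms do not differ.** Azacitidine + 28 sets the end in Arm A when last durvalumab + 90 ≤ last azacitidine + 28. That is when durvalumab stopped at least 90 − 28 = 62 days before the last azacitidine dose.

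**Group-level size, if this exposure were the AESI denominator (deaths only).**
- Let W be the window measured from the last azacitidine dose: 28 days in Arm B and 91 − 7 = 84 days in Arm A.
- With constant hazard L, the expected days after death are W − (1 − exp(−L·W))/L.
- Understatement = expected days after death divided by uncapped exposure.
- Assumed time from first to last dose: 140 days. Uncapped exposure is then 168 days in Arm B and 224 in Arm A.
- L = ln 2 / median survival, using 10.4 months for AML (protocol 1.3.3) and 24.46 months for MDS (protocol 1.3.2), at 30.4375 days per month (SAP 5.1.2).

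| | L per day | Arm B | Arm A |
|---|---|---|---|
| AML | 0.00219 | 0.84/168 = 0.50% | 7.27/224 = 3.25% |
| MDS | 0.00093 | 0.36/168 = 0.22% | 3.20/224 = 1.43% |

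At 250 days from first to last dose these fall to 0.30% v 2.18% (AML) and 0.13% v 0.96% (MDS).

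Mortality just after treatment stops may exceed the average hazard. With 140 days and an assumed 28-day mortality after the last azacitidine dose of 5% / 10% / 20% / 30%, the understatement is 0.4% / 0.8% / 1.7% / 2.6% in Arm B and 2.7% / 5.3% / 10.2% / 14.5% in Arm A. The documents give no value for that mortality.

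**The case against.** The strongest objection is to the AESI consequence. A reader might infer that the safety comparison will be biased in favour of the combination, on the ground that the SAP 8.1 exposure is the only person-time available. The documents do not support that. SAP 12.1 names no denominator, and SAP 8.1 itself supplies an alternative: duration of treatment, defined per drug and capped at death. AESIs are summarised separately for each drug, which suits a per-drug time. So the effect on rates is conditional. Against this, the SAP 8.1 exposure matches the window for treatment-emergent events and SAP 9.1 uses the same interval as its study treatment exposure period, so a programmer could reasonably choose it.

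A second tempting reading is to carry the single-subject figures over to the group. A death in Cycle 6 can inflate one Arm A subject's exposure by 70 days or more, but a double-figure effect on the arm's rate would need a large share of subjects to end that way. The documents give no such share.

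Third, the + 28 and + 90 days are not wrong in themselves. For subjects alive and followed through the window they agree with the safety follow-up and the event-counting window.

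Fourth, the primary analysis follows completion of 6 cycles by all subjects, so a cut-off part-way through an early cycle does not arise there. Subjects who continue past Cycle 6 can still be credited with time after cut-off, but over a longer exposure.

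Fifth, the SAP's own precedents in these definitions cap at death only; adding the cut-off is an extension of them. It is still needed, because unobserved days are not exposure available to the analysis.

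These points limit the consequence. None justifies counting days after death.

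**Conclusion.** The defect is a stated rule that gives a wrong number, not merely missing detail: the exposure table by arm will include time after death, and time after cut-off for subjects on treatment. It conflicts with the death caps in SAP 5.1.3 and in the duration-of-treatment formula of SAP 8.1. The excess is larger in Arm A whenever durvalumab was given within 62 days of the last azacitidine dose and the subject dies or reaches the cut-off before the durvalumab window closes.

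An effect on the AESI rates follows only if this exposure is the denominator. Its size is then modest from deaths alone, on the constant-hazard and 140-day assumptions above. It is larger if many subjects die early or are still on treatment at cut-off. AESI incidence proportions, cumulative dose, number of cycles and dose intensity do not use the 28- or 90-day exposure extension and are unaffected by it. The change should be made, but it does not touch the primary analysis.

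**What to change.** In SAP 8.1, end treatment exposure at the earliest of the 28- or 90-day window end (the later of the two in the combination arm, as now), the date of death and the data cut-off, or last contact if the subject is lost to follow-up. In SAP 12.1, state that the AESI person-years use this capped time.

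SAP 9.1 can stay as it is: its interval only classifies medications that were recorded, so capping it would change little.

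The cost is SAP wording and one line of derivation from dates already collected. Reported exposure becomes slightly shorter.
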